4.1.3 Number of subjects

106 subjects will be included in the investigation in order to have 100 evaluable subjects. The justification for the number of subjects is described in section 'Statistical considerations'.

4.2 Subject enrolment and Informed consent

Before a subject is asked to sign an informed consent form an investigator must explain the following to the potential investigational subject :

- The rationale, aims and objectives of the investigation
- Risks and benefits
- Alternative treatments
- Extent of the subject's involvement
- That the subject can withdraw his/hers consent at any time
- That the confidentiality of patient data will be maintained at all time

The subject must have the possibility to ask any questions. Signed and dated informed consent from potential subjects must be obtained before any investigational procedure can be performed. The

investigator will after informed consent has been obtained, assign a unique enrolment number to the subject.

4.3 Randomisation

Subjects will be randomised to either:

- **Test group:** Minimally invasive surgery and the use of Cochlear Baha BA400 Abutment (investigational device).
- or
- **Control group:** Traditional surgery and the use of Cochlear Baha BA300 Abutment (comparator).

Randomisation will be performed in a proportion 1:1 ratio (test group/control group) at visit 2, i.e. the day of surgery, stratified for site with unknown block size.

Randomisation will be based on optimal allocation using a Web-based application.

If a subject discontinues participation in the investigation (see Section 'Discontinuation') his/her randomisation code/subject number will not be re-used. Discontinued subjects are not allowed to re-enter into the investigation.

4.4 Discontinuation

- Subjects are free to discontinue their participation in the investigation at any time
- Subjects may be discontinued from the investigation at any time at the discretion of the investigator

Subjects who themselves discontinue from the investigation should always be asked about the reason(s) for the discontinuation and the presence of any adverse events. If possible, the subject should always be seen and assessed by an investigator. Any adverse event should be followed up.

4.5 Replacement of subjects

If a subject discontinues participation in the investigation, he/she will not be replaced.

4.6 Insurance

In case of any damage or injury occurring during the participation in the investigation, the Sponsor has contracted an insurance company, Willis, which will cover the liability of the Sponsor, the investigators and other persons involved in the investigation. The Sponsor may use a local insurance company, where applicable, according to national legislation.

5 Design of the clinical investigation

The investigation is designed as an international multicentre, open, randomised, comparative, parallel group, prospective clinical investigation. A one year investigation with a two year follow-up.

5.1 Rationale for the design of the clinical investigation

This investigation is designed to evaluate the approved surgical techniques and the two abutments whit the standard procedures when it comes to fitting the sound processor and the follow-up visits at the clinics remains the same.

The rationale for a one year investigation is that within this time period the initial wound healing has occurred, the patients are used to live with the sound processor and that problems with the scar (inflammation/infection) normally has occurred. In order to collect long-term data a two year follow-up has been added to the initial investigation.

In order to have a fair comparison the patients will be randomised to one of the two treatments.

5.2 Variables

5.2.1 Primary efficacy variables

The first primary endpoint, a combined endpoint of infection/inflammation, overgrowth, pain and numbness will be evaluated, as the sum of the following four events:

1. Holgers Index ≥ 2 any time between 3 weeks to 1 year
2. Any overgrowth any time between 3 weeks to 1 year
3. Pain (scar/neuropathic) according to POSAS ≥ 3 any time between 3 weeks to 1 year
4. Any numbness any time between 3 weeks to 1 year

The second primary endpoint: direct medical cost associated with the surgery (time to perform surgery, number of wound dressings sessions and cost to treat complications) will be calculated for each subject using standard cost/unit in each participating country.

5.2.2 Secondary efficacy variables

The secondary efficacy variables will be evaluated as follows:

- Infections/inflammations will be evaluated by the Holgers Index
- Soft Thickening/overgrowth scale (0-2)
- Wound healing will be evaluated by the surgeon/surgical nurse.
- Numbness (paraesthesia) – the patients will indicate if they experience numbness and the area where they have the problem on a scale from 0-2.
- Pain in the scar area and neuropathic pain will be evaluated by the patient using ‘The Patient and Observer Scar Assessment Scale (POSAS)’ (1-10)
- Aesthetics will be evaluated by the subject and the surgeon using ‘The Patient and Observer Scar Assessment Scale (POSAS)’(two scales):
 - Patient aesthetic scale (1-10)
 - Observer aesthetic scale (1-10)
- Surgery time (min)

5.2.3 Tertiary efficacy variables

Improved quality of life when receiving a Baha will be evaluated by:

- A generic quality of life scale - Health Utility Index (HUI)
 - HRQL score for overall health
 - Vision score
 - Hearing score
 - Speech score
 - Ambulation/mobility score
 - Dexterity score
 - Self-care score
 - Emotion score
 - Cognition score
- A disease specific quality of life scale - Abbreviated Profile of Hearing Aid Benefit (APHAB)
- Usage of the Baha (sound processor)
- Implant stability (ISQ)
- Visual abutment length

5.2.4 Safety variables

- Loss of implant
- Adverse Events
- Serious Adverse Events
- Device deficiency

5.2.5 Demographics and baseline variables

- Age
- Gender
- Ethnical background
- Medical and surgical history
- Current medications and treatments
- Type of hearing loss
- Skin thickness
- Length of abutment
- Nicotine use

5.2.6 Concomitant medications and treatments

- Use of concomitant medications and nicotine
- Use of concomitant treatments

5.3 Investigational flow chart

Table 1: Flow chart

Procedures and timing	Visit 1 Baseline	Visit 2 Surgery	Visit 3	Visit 4	Visit 5	Visit 6	Visit 7	Visit 8	Visit 9	Visit 10
Day/Week/Month ¹	Before day of surgery	D 0	D 10	W 3	W 6	W 12	W 24	M 12	M 24	M 36
Time window			± 4d	± 1w	± 1w	± 2w	± 4w	± 4w	± 6w	± 6w
Demographics	X									
Medical history	X									
Eligibility criteria	X									
Informed consent	X									
Randomisation (see 4.3.)		X								
Skin thickness (see 6.1)		X								
Length of abutment (see 6.1)		X								
Implant surgery (see 6.2)		X								
Time to perform surgery		X								
Implant stability		X	X	X	X	X	X	X	X	X
Suture removal (see 6.3)			X							
Wound healing			X	X	X	X	X			
Baha installation (see 6.4)				X						
Use of sound processor ²					X	X	X	X	X	X
Change of abutment (see 6.5)			X	X	X	X	X	X	X	X
Loss of implant			X	X	X	X	X	X	X	X
Holgers index			X	X	X	X	X	X	X	X
Soft tissue thickening/overgrowth			X	X	X	X	X	X	X	X
Visible abutment length			X	X	X	X	X	X	X	X
Aesthetic evaluation surgeon						X		X		
Aesthetic evaluation incl. pain question (POSAS) ³						X		X		
Pain ^{2, 3}			X	X	X		X			
Numbness			X	X	X	X	X	X	X	X
Use of nicotine ²	X			X		X		X	X	X
Health Utility Index ²	X						X	X		
Abbreviated Profile of Hearing Aid Benefit ²	X						X	X		
Extra visits (see 6.6)			X	X	X	X	X	X		
Concomitant treatment			X	X	X	X	X	X		
Concomitant medication			X	X	X	X	X	X		
Device deficiency		X	X	X	X	X	X	X	X	X
Adverse events		X	X	X	X	X	X	X		
ADE									X	X

¹ The time between visits will be calculated from visit 1 (time 0)

² To be completed by subject on questionnaires

³ Pain question included in the POSAS scale

6 Procedures

6.1 Skin thickness and length of abutment

6.1.1 BA300 abutment

The 6 mm pre-mounted abutment on the 4mm implant is for standard use. The 9mm pre-mounted abutment on the 4mm implant is for patients with thicker scalps or if regrowth of subcutaneous tissue is anticipated.

6.1.2 BA400 abutment

The surgeon should measure the tissue thickness before local anaesthesia is infiltrated. A hypodermic needle, a clamp and a ruler may be used. Thereafter an abutment should be selected depending on the tissue thickness

Tissue thickness (mm)	Abutment length (mm)
≤ 4	6
5	8
6	8
7	10
8	10
9	12
10	12
>10	12

6.2 Surgery

Subjects will be randomised to either:

- **Test group:** Minimally invasive surgery and the use of BA400 abutments.

Selection of abutment length and surgery shall be performed in accordance with the procedure for FAST (one-stage) surgery described in the Surgery Guide.

In brief, the surgical procedure consists of making a small straight incision through the skin at the planned implant site to access the bone and insert a 4 mm implant with a pre-mounted BA400 abutment of adequate length. After placing the implant and abutment, the incision is sutured back around the abutment ensuring skin edges are everted and in contact with the coated part of the abutment. No removal of soft tissues shall be performed, unless the skin is too thick to accommodate a 12 mm abutment, in which case some adipose tissue may be removed, as described in the Surgery Guide. After closing the incision, suitable dressing and a healing cap shall be used.

or

- **Control group:** Standard surgery and the use of BA300 abutments.

Surgery shall be performed in accordance with the procedure for FAST (one-stage) surgery described in the Surgery Guide.

Soft tissue reduction at the selected implant site shall be performed using either a dermatome technique or a manual technique (e.g. linear or u-shaped incision). The amount of soft tissue removal shall be in accordance with the guidelines provided in the Surgery Guide. A 4 mm implant with a pre-mounted BA300 abutment shall be inserted. The skin flap shall be sutured

back in place ensuring that it sits tight to the bone and periosteum. A biopsy punch may be used to create a hole for the abutment through the skin flap. Wound dressing and healing cap shall be applied following the recommended procedure in the Surgery Guide.

6.3 Removal of sutures

The sutures will be removed at visit 3 (i.e. 10 days after surgery). The surgeon/surgical nurse will determine if the wound requires further wound dressings, and if so, extra visit(s) will be scheduled, until the wound is considered healed.

The subject will receive instruction how to take care of skin around the abutment in accordance with local practice.

6.4 Baha sound processor installation

A Baha sound processor will be installed to the implant at visit 4 (i.e. 3 weeks after surgery). If the wound is not considered sufficiently healed, as judged by the surgeon/surgical nurse, the installation shall be delayed to a scheduled subsequent visit or extra visit, when the site is considered sufficiently healed.

6.5 Change of abutment

If, during the course of the study, the surgeon needs to change the abutment, the subject should receive an abutment in accordance with the randomisation, i.e. test device or comparator. The type and size of abutment, the reason for the abutment change, and any concomitant treatment and/or medication provided to the subject at the time of abutment change should be recorded in the case report form (CRF).

If the abutment is changed to a longer or shorter abutment during the investigation, ISQ values shall be recorded by resonance frequency analysis according to the procedure described in section 7.3.13

6.6 Extra visit(s)

Extra visit(s) may be a scheduled visit to change the wound dressing or to follow-up any complications. These visits will be recorded on extra pages in the CRF. The following information will be recorded:

- Date
- Reason for extra visit
- Staff that conducted the visit (surgeon, surgical nurse or audiologist)
- Time to perform the visit
- Material used

Subjects will be encouraged to contact the clinic for follow-up if anything out of the ordinary occurs, e.g. local reaction, loss of the implant

7 Assessments

7.1 Subject demographics

The following demographic data will be recorded at inclusion:

- Date of birth (month and year)
- Gender
- Ethnical background
- Use of nicotine

7.2 Medical history

The following subject characteristics will be recorded at inclusion:

- Relevant medical and surgical history as judged by the investigator
- Current concomitant medication and treatments
- Type of hearing loss (conductive or mixed hearing loss or single-sided sensorineural deafness)

7.3 Efficacy variables

[figure not shown]
7.3.1 Holgers index

The Holgers Index¹² is designed to capture signs and symptoms of inflammation or infection at the site of implantation. The scale should be completed at visit 3-10.

The following scale will be used:

- 0 No irritation. Epidermal debris removed, if present
- 1 Slight redness. Local temporary treatment, if needed
- 2 Red and slightly moist tissue. No granulation formation, local treatment and extra controls as indicated*
- 3 Reddish and moist; sometimes granulations tissue, revision surgery is indicated*
- 4 Removal of the abutment / implant necessary due to infection*
- R Removal of implant for reasons not related to skin problems*

* Should also be reported on the AE page in the CRF.

7.3.2 Soft tissue thickening/overgrowth scale

In order to capture soft tissue thickening/overgrowth the following scale has been developed for this investigation. The scale should be completed at visit 3-10.

The following scale will be used:

- 0 No soft tissue thickening or overgrowth
- 1 Slight soft tissue thickening or overgrowth
- 2 Moderate soft tissue thickening or overgrowth. Local treatment and extra controls as

indicated*

3 Marked/distinct soft tissue thickening or overgrowth. Revision surgery is indicated.*

* Should also be reported on the AE page in the CRF

7.3.3 Direct medical cost

7.3.3.1 Time to perform surgery

The time to perform surgery will be recorded as “skin to skin” time, i.e. the time from first skin incision until finishing suturing the wound. Also the attending staff and type of anaesthesia will be recorded.

7.3.3.2 Number of dressings

The total number of wound dressings performed, i.e. number of extra visits, duration of visit, staff that conducted the visit, and material used.

7.3.3.3 Treatment of complications

[figure not shown]
All resources used to treat complications will be recorded, e.g. extra visits, type of treatment (e.g. local treatment, re-surgery, etc), and concomitant medication.

7.3.4 Wound healing

A surgeon or a surgical nurse will at visit 3-7 determine if the wound is healed or not healed.

7.3.5 Visible abutment length

The visible abutment length (from skin to top of the abutment) will be measured at visit 3-10 using a ruler. The ruler must be appropriately cleaned before use, by using Isopropanol (99,7%).

7.3.6 Aesthetic evaluation

The aesthetic outcome of the surgery will be evaluated by the subject and the surgeon at visit 6 and 8. The scar will be evaluated in accordance with the Patient and Observer Scar Assessment Scale (POSAS) v 2.0¹³ that consists of two parts, a patient scale and an observer scale:

- The patient scale contains six items (pain, itching, color, stiffness, thickness and irregularity) that should be scored 1-10, with 10 indicating the worst imaginable scar or sensation.
- The observer scale also contains six items (vascularity, pigmentation, thickness, relief, pliability and surface area) that should be scored 1-10. Besides the 10-step scale, category boxes are available to score nominal parameters (e.g. type of color).
- Both the patient and the observer should finally score the overall opinion of the scar on the 1-10 scale.

7.3.7 Pain

The pain question available in the POSAS scale will be completed by the subjects also at visit 3, 4, 5 and 7 in addition to visit 6 and 8 when all items will be rated on the POSAS scale.

The subject will rate the following question 'has the scar been painful the past few weeks' on the 1-10 scale where 1= no, not at all and 10=yes, very much.

A second pain question will be added to the POSAS scale 'have you had any neuropathic pain during the past weeks'. The same scale as above applies. Investigational staff will explain the meaning of the term 'neuropathic pain' before the patient will complete the questionnaire.

7.3.8 Numbness

Subjects will be asked if they experience any numbness around the abutment at visit 3-10. The following scale will be used:

1. No numbness
2. Numbness within 2 cm from the abutment
3. Numbness within and beyond 2 cm from the abutment

7.3.9 Health Utilities Index Mark 3 (HUI3)

The Health Utilities Index (HUI®) is a generic preference-based system for measuring comprehensive health status and health-related quality of life (HRQL). HUI® provides descriptive evidence on multiple dimensions of health status, a score for each dimension of health, and a HRQL score for overall health. Health dimensions include vision, hearing, speech, ambulation/mobility, pain, dexterity, self-care, emotion and cognition. Each dimension has 3-6 levels. The subjects will complete the HUI3^{14, 15} at visit 1, 7 and 8.

7.3.10 The Abbreviated Profile of Hearing Aid Benefit (APHAB)

The Abbreviated Profile of Hearing Aid Benefit (APHAB)¹⁶ is a 24-item self-assessment, disability-based inventory that can be used to document the outcome of a hearing aid fitting, to compare several fittings, or to evaluate the same fitting over time. The subjects will complete the APHAB at visit 1, 7 and 8

7.3.11 Information recorded during surgery

The following information should be recorded during surgery:

- Type of surgery
- Skin thickness (skin thickness should not be measured in the control group since it is not in accordance with the surgical procedure when soft tissue reduction is performed)
- Length of the abutment
- Implant stability

7.3.12 Use of sound processor

The subjects will be asked at visit 6-10 how many days a week and hours per day they use the sound processor. Also the type of sound processor will be registered.

7.3.13 Implant Stability Quotient (ISQ)

ISQ will be measured at surgery as a baseline value and at visit 2-10.

The resonance frequency analysis renders an Implant Stability Quotient (ISQ) value ranging from 1 to 100. Measurements shall be performed at the abutment level. The highest and lowest ISQ value out of two perpendicular measurements obtained at each time point shall be recorded, ISQ High and ISQ Low.

The Osstell ISQ instrument and SmartPeg Type 55 (Osstell, Gothenburg, Sweden) shall be used. The procedure for obtaining ISQ values is described in the manufacturer's instruction.

7.3.14 Smoking habits

The subjects will at visits 1, 4, 6, 8, 9 and 10 complete a questionnaire regarding the use of nicotine:

	Subject response	
1	Does not smoke	
2	Less than 10 cigarettes/day	Low consumption
3	Between 11 and 20 cigarettes/day	Medium consumption
4	Between 21 and 40 cigarettes/day	High consumption
5	More than 40 cigarettes/day	Very high consumption

In Sweden a large proportion of adults use another form of tobacco, wet snuff. In the Swedish questionnaire the subjects will be asked if they use wet snuff and if so, the type of product and the quantity used per day.

7.4 Safety variables

7.4.1 Loss of implant

The loss of implant is defined as the actual loss of the implant from the site of implantation and will be recorded from visit 2 and onwards.

7.4.2 Device deficiency reporting

The definition of a device deficiency is an inadequacy of a medical device with respect to its identity, quality, durability, reliability, safety or performance.

A device deficiency should be reported to the sponsor. A device deficiency that could have lead to a Serious Adverse Event (SAE) should be reported immediately (see next section).

7.4.3 Adverse Event (AE) and Serious Adverse Event (SAE)

Term	Definition
Adverse Event (AE)	Any untoward medical occurrence, unintended disease or injury, or untoward clinical signs (including abnormal laboratory findings) in subjects, users or other persons, whether or not related to the investigational medical device
Adverse Device Effect (ADE)	Adverse event related to the use of an investigational medical device

Serious Adverse Event (SAE)	
Adverse event that
 
a) led to death
 
b) led to serious deterioration in the health of the subject, that either resulted in
 
 • a life-threatening illness or injury • a permanent impairment of a body structure or a body function • in-patient or prolonged hospitalization • medical or surgical intervention to prevent life-threatening illness or injury or permanent impairment • to a body structure or a body function 
c) led to foetal distress, foetal death or a congenital abnormality or birth defect
 
Note - Planned hospitalization for a pre-existing condition, or a procedure required by the CIP, without serious deterioration in health, is not considered a serious adverse event.

Serious Adverse Device Effect (SADE)	Adverse device effect that has resulted in any of the consequences characteristic of a serious adverse event
Unanticipated Serious Adverse Device Effect USADE	Serious adverse device effect which by its nature, incidence, severity or outcome has not been identified in the current version of the risk analysis report

7.4.3.1 Handling and reporting of AEs and ADEs

Subjects will be carefully monitored during the investigation for possible adverse events and appropriate treatment of the subject will be initiated.

Any adverse events observed will be fully investigated by the investigator and documented in the case report form (CRF) including assessment of severity (mild, moderate or severe) and relationship to the medical device.

At visit 9 and 10 (week 101 and 156) only ADEs needs to be reported.

7.4.3.2 Handling and reporting of SAEs and device deficiency that could have lead to a SAE

An investigator should report within 24 hours, after being aware of the event, an SAE or a device deficiency that could have lead to a SAE. The report should be faxed or sent as a mail attachment to Cochlear Bone Anchored Solutions AB. Contact information is available on the SAE form.

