4.3 Safety Variables

- Time to Loss of implant
- Adverse Events
 - Adverse Event (AE)
 - Adverse Device Effect (ADE), defined as AE with Probably or Definitely related to Study product
 - Serious Adverse Event (SAE)
 - Serious Adverse Device Effect (SADE), define as SAE with Probably or Definitely related to Study product
- Device deficiency by visit and divided by Not leading to SAE, Did lead to SAE and could have led to SAE.
- Removal of abutment

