5.8 Safety Analyses

5.8.1 *Loss of implant*

The loss of implants will be analysed with the Log-rank test between the two treatment groups and illustrated with Kaplan-Meier survival curves. The survival probabilities at 90 days, 180 days and at 365 days (from the KM-estimates) will be tabulated. Cox proportional Hazard ratio (with 95% CI) of implant loss for treatment group will be presented. Number of loss of implant and total follow up time per treatment group will be presented. Based on these numbers simulations (Markov-Modelling) of different scenarios will be made.

5.8.2 *Adverse Events*

Only treatment-emergent AEs will be included in the summaries for safety population.

A summary of subjects reporting at least one of the following AEs will be presented in an overview table:

- Any AE
- Any SAE
- Any treatment-related AE (Probably + Definitely)
- Any treatment-related SAE (Probably + Definitely)
- Death

Summaries per System Organ Class (SOC) and Preferred Term (PT) presenting n of AEs and n (%) of subjects with at least one AE will be provided for:

- All AEs (includes all serious and non-serious AEs)
- All AEs by Severity
- All AEs by Relation to Treatment
- All SAEs

5.8.3 *Device deficiency*

Number of Device Deficiencies and number and percentage of patients with a Device Deficiency.

5.8.4 *Removal of abutment*

Number and percentage of removal of abutment will be presented by treatment group.

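### The SAP's adverse event tables run undivided to 3 years, but after month 12 routine reporting narrows to adverse device effects, which the protocol and SAP define differently

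*Protocol*

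**What the plan says.** **Collection.** Both protocol flow charts (synopsis and 5.3) and the SAP schedule mark adverse events at visits 2 to 8 and replace that row with ADE at visits 9 and 10. Protocol 7.4.3.1 says the same: "At visit 9 and 10 (week 101 and 156) only ADEs needs to be reported". Extra visits, concomitant treatment and concomitant medication also stop at visit 8. Implant loss, device deficiency, Holgers index, overgrowth and numbness continue to visit 10 in both arms.

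**Other rules on the same events.** Protocol 7.4.3.2 has its own SAE rule, with no end date and no relatedness condition: "An investigator should report within 24 hours, after being aware of the event, an SAE". Protocol 7.3.1 and 7.3.2 schedule the Holgers and overgrowth scales at visits 3 to 10 and say of the higher grades (Holgers 2 to 4 and R, overgrowth 2 and 3): "Should also be reported on the AE page in the CRF". Neither section sets a visit limit or a causality condition for this.

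**Definition.** Protocol 7.4.3 defines an ADE as "Adverse event related to the use of an investigational medical device". Protocol 4.3 labels BA400 the investigational device and BA300 the comparator. SAP 4.3 has an ADE "defined as AE with Probably or Definitely related to Study product".

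**Analysis.** SAP 5.8.2 says: "Only treatment-emergent AEs will be included in the summaries for safety population". It lists any AE, any SAE, treatment-related events and deaths, then all AEs by class, severity and relation. No period is given and the treatment-emergent window has no end. SAP section 6 sets the main analysis at 12 months with an update at 3 years. SAP section 1 excludes only the 3-year health economic evaluation, so 3-year safety falls under this SAP.

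**The concern.** The AE tables assume one ascertainment rule, and collection has two: all AEs in year 1, then only those judged device-related in years 2 and 3. If the same tables are rerun at 3 years, their non-serious rows add complete counts to filtered ones. A reader would take the result as 3-year incidence and would see too few events.

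The trial is open, so an unblinded relatedness judgement decides whether a late non-serious event is recorded at all. What counts as related also depends on which document the site follows. Protocol 5.1 says the two extra years were added to collect long-term data, and Protocol 1.3.3 names adverse events in the safety evaluation, so these tables serve a stated purpose.

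**Working it through.** The plan states no figure to reproduce here. The check is a comparison of rules plus simple exposure arithmetic.

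**1. Time under the narrower rule.** Follow-up is 36 months and full AE collection ends at month 12: (36 − 12)/36 = 24/36 = 67%. For the 106 planned subjects with no dropout, that is 106 × 2 = 212 of 106 × 3 = 318 person-years. This is a share of time, not of missed events.

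**2. Effect on a pooled 3-year AE row.** Let r be the yearly AE rate, assumed constant, and f the share of AEs that are device-related. Year 1 records r and years 2 and 3 record 2fr, against a true total of 3r. The captured share is (1 + 2f)/3. The documents give no value for f, so a range is shown:

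| Assumed f | Captured share |
|---|---|
| 0.10 | (1 + 0.20)/3 = 0.40 |
| 0.25 | (1 + 0.50)/3 = 0.50 |
| 0.50 | (1 + 1.00)/3 = 0.67 |
| 0.75 | (1 + 1.50)/3 = 0.83 |

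SAEs and higher Holgers or overgrowth grades that reach the AE page by their own rules would raise these shares. They are illustrations with those routes left out.

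**3. Effect of the ADE definition.** If a site took the protocol wording literally and recorded no late ADE for BA300, equal true rates would give counts of r(1 + 2f) against r. The test-to-control ratio would be 1 + 2f: 1.2, 1.5, 2.0 and 2.5 for the four values of f, and 3.0 for ADEs alone. Under the SAP's study-product wording the ratio is 1 and only the undercount in step 2 remains.

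**4. The rules side by side.**
- Protocol 7.4.3.1 limits visits 9 and 10 to ADEs, while 7.3.1 and 7.3.2 send higher grades to the AE page at the same visits whatever the cause. A higher grade at month 24 judged unrelated to the device is reportable under one rule and not under the other.
- 7.4.3.1 concerns AEs and ADEs, and 7.4.3.2 concerns SAEs. They fit together if the ADE limit applies only to non-serious events, but the text does not say so.
- The SAP adds a probability threshold to the ADE definition that the protocol lacks, and SAP section 7 does not list this as a change.

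**5. Editorial.** Protocol 7.4.3.1 puts visit 9 at week 101; 24 × 365.25/12/7 = 104.4 weeks.

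**The case against.** A reader might infer three stronger points, and the documents do not support them.

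*Late safety data come from the test arm only.* This follows from a literal reading of Protocol 7.4.3 with 4.3, but much else points to both arms. The causality item in 7.4.3.1 refers neutrally to the medical device. The ADE rows carry no arm restriction. The SAP speaks of the study product. Protocol 8.2 uses the ADE term in comparing BA400 with BA300. The AE definition contains the same investigational-device phrase and is plainly meant for everyone. The BI300 implant is part of both arms' devices. One-arm collection is therefore a possible misreading, not an established fact, and the ratios in step 3 describe only that case.

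*SAE and death counts are incomplete after month 12.* The SAE rule is separate and open-ended, and death is an SAE criterion. The natural reading is that these rows are complete to month 36; confirmation is needed, not new collection.

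*Nothing but ADEs is collected.* Implant loss, device deficiency, Holgers, overgrowth and numbness all run to visit 10 in both arms, so the main expected late site complications are covered.

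It is also fair to say that narrower AE reporting in a declared follow-up phase of CE-marked devices is a legitimate choice, and that the SAP already tabulates AEs by relation to treatment.

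What survives is narrower. The continuing scales do not supply other non-serious AEs. A SAP definition applied after collection cannot restore unreported events. A relation-to-treatment table does not separate the two collection periods, and the 12-month analysis does not protect the 3-year update.

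**Conclusion.** The point holds in limited form. As written, the non-serious AE rows of the 3-year update combine full year-1 ascertainment with a causality-filtered subset over 67% of planned follow-up, and cannot be interpreted as 3-year rates. The undercount depends on the device-related share: on the assumptions in step 2, capture would be about 40% to 83%. Between-arm distortion arises only if sites applied the protocol's ADE wording literally, which other wording argues against.

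The 12-month main analysis lies within full AE collection, and both primary endpoints close at one year, so neither is affected. This should be corrected before the 3-year tables are produced, but it does not threaten the trial's main conclusions.

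**What to change.** 1. **SAP 5.8.2 and Tables 14.3.2.1 to 14.3.2.5:** tabulate 0–12 and 12–36 months separately, with exposure by arm. Limit the any-AE row to 0–12 months; for 12–36 months show only the classes actually collected.
2. **Protocol 7.4.3 and SAP 4.3:** use one ADE definition that covers the assigned study device in both arms, with one relatedness threshold. State whether the implantation procedure is included, since the randomised comparison is device plus procedure.
3. **Protocol 7.4.3.1:** reconcile with 7.4.3.2 by confirming that all SAEs are reportable to month 36, and with the AE-page rule in 7.3.1 and 7.3.2. Correct the visit 9 week number.

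**Cost.** The table split is SAP wording applied to existing outputs, and it works even if visits 9 and 10 are complete. Items 2 and 3 need a protocol amendment with ethics approval (Protocol 2.1.3) and a few more AE pages, and help collection only if those visits are still to come. The SAP already describes randomisation in the past tense, so some may have passed; in that case the report should state which ADE definition sites used.
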